### **2.2 Study objectives**

#### **Objectives of the main study period**

1. To compare the efficacy of BCD-085 in two dosing regimens and placebo using PASI 75 rate, sPGA score, and other secondary efficacy measures after 12 weeks of the treatment.
2. To compare the efficacy of BCD-085 in two dosing regimens and placebo using PASI 75 rate, sPGA score, and other secondary efficacy measures after 52 weeks of the treatment.
3. To evaluate the proportion of patients in each study arm who developed adverse events with repeated administration of BCD-085 or placebo. To compare the safety profiles of BCD-085 Q4W and BCD-085 Q2W.
4. To assess the immunogenicity of BCD-085 defined as the proportion of patients who developed anti-drug antibodies (binding/neutralizing).

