#### **4.1.2 Secondary endpoints**

##### **Efficacy endpoints during the main study period (Week 0 through Week 54):**

- Proportion of patients who achieved PASI 75/90/100 at Weeks 8, 16, 24, 42 and 52, by study arms.
- Proportion of patients with sPGA score 0 or 1 at Weeks 8, 12, 16, 24, 42, and 52.
- Proportion of patients with sPGA score 0 at Weeks 16, 24, 42, and 52.
- Relative change from baseline in PASI score at Weeks 8, 12, 16, 24, 42 and 52.
- Change from baseline in itch severity measured with visual analog scale (0 mm to 100 mm) at Weeks 1, 12, 24, and 52.
- Change from baseline in Nail Psoriasis Severity Index (NAPSI) score at Week 12, 24, and 52.
- Change from baseline in Dermatology Life Quality Index (DQLI) score at Weeks 8, 12, 24, 42, and 52.
- Proportion of patients with DLQI score 0 or 1 at Weeks 24, 42, and 52.
- Proportion of patients (among those with psoriatic arthritis) who achieved an ACR20/50/70 at Weeks 12, 24, and 52.

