**Main study period (Week 0 to Week 54)**

In this study period patients will be distributed to three arms:

- **Arm 1:** Patients in this arm (85 subjects) will receive BCD-085 120 mg (two subcutaneous injections, 60 mg in 1.0 mL each) once a week during the first 3 weeks (induction) and then once every 2 weeks through Week 10. Thus, the investigational product will be administered on Day 1 of Week 0, Week 1, Week 2, Week 4, Week 6, Week 8, and Week 10.
- **Arm 2:** Patients in this arm (85 subjects) will receive BCD-085 120 mg (two subcutaneous injections, 60 mg in 1.0 mL each) once a week during the first 3 weeks (induction) and then once every 4 weeks through Week 10. Thus, the investigational product will be administered on Day 1 of Week 0, Week 1, Week 2, Week 6 and Week 10. To maintain the study blind, patients of this arm will receive placebo (2 injections) on Day 1 of Week 4 and Week 8.
- **Arm 3:** Patients of this arm (43 subjects) will receive placebo (2 subcutaneous injections of placebo, 1.0 mL each) on Day 1 of Week 0, Week 1, Week 2, Week 4, Week 6, Week 8 and Week 10.

On Week 12, the treatment efficacy will be assessed with a PASI 75 score, and the treatment will be **unblinded**. Patients from Arms 1 and 2 will be given BCD-085 once every 4 weeks. Patients from Arm 3 will receive BCD-085 as follows:

- ✓ Induction: Weeks 12, 13, and 14, once a week;
- ✓ Weeks 18 through 50: once every 4 weeks.

Therefore, there will be 3 arms even after unblinding, and patients will receive BCD-085 according to the regimens described below:

- a) Patients in Arm 1 will receive BCD-085 120 mg (2 SC injections of 60 mg each) once every 4 weeks starting from Week 14 and through Week 50.
- b) Patients in Arm 2 will receive BCD-085 120 mg (2 SC injections of 60 mg each) once every 4 weeks starting from Week 14 and through Week 50.
- c) Patients in this arm will receive BCD-085 120 mg once a week at Weeks 12, 13, 14, then once every 4 weeks through Week 50.

Unblinding will be performed at Visit 8 (Week 12) by opening the randomization envelopes provided by the Sponsor with the investigational products.

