#### **4.3.5. Blinding and subject-specific lots of investigational products**

In the first, blinded, period of the study (until Week 12), neither investigators nor patients will know whether the active drug (BCD-085) or placebo is used.

The investigator (the principal investigator, a member of the study team responsible for the treatment of this patient) will receive BCD-085/placebo in identical secondary packaging (cartons). Each product will have an individual lot number. Each lot number is patient-specific.

Once the patient is enrolled in the study (randomized), the Sponsor will send to the investigator the Subject ID and appropriate lot number of the drug to be given to this patient. If the electronic randomization system is used, all numbers are generated automatically after the investigator enters all the required information. The investigator records the lot numbers in the source documents and the eCRF.

Starting from Week 12 treatment arms will be unblinded. The investigators and patients will be made aware of the drug and the dose used. There will be no individual lots during this study stage. Batch number should be recorded. Unblinding will be performed at Visit 8 (Week 12) by opening the randomization envelopes provided by the Sponsor with the investigational products.

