Appendix 1.

Translated from Russian to English, dated 26-Nov-2019

Visit	Screening	1	2	3	4	5	6	7	8	8-1 	9	10	11	12	13	14	15	16	17	18	19	20	21	22	
Week	Week -4 to Week 0 (28 days)	Week 0	Week 1	Week 2	Week 4	Week 6	Week 8	Week 10	Week 12	Week 13	Week 14	Week 16	Week 18	Week 22	Week 24	Week 26	Week 30	Week 34	Week 38	Week 42	Week 46	Week 50	Week 52	Week 54	
Day		1	1	1	1±3	1±3	1±3	1±3	1±3	1	1±3	1±3	1±3	1±3	1±3	1±3	1±3	1±3	1±3	1±3	1±3	1±3	1±3	1±3	
Chest X-ray 	+																								+
Pregnancy test 	+																								+
Inclusion/exclusion criteria	+																								
Inclusion in the study (randomization and stratification)	+																								
Administration of the investigational product 		+	+	+	+	+	+	+	+ 	+	+	+	+	+	+	+	+	+	+	+	+	+	+	+ 	
Training on the procedure of subcutaneous injection																									+ 

 Chest fluorography can be used instead of chest X-ray. Screening chest X-ray is not required if the patient had chest X-ray/fluorography/CT/MRI done within 3 months before signing the ICF for this study.

 Pregnancy test detecting hCG in the urine (test strips). Pregnancy test is not required if the female patient is at least 2 years post-menopausal or had a uterus or ovary surgery that makes pregnancy impossible.

 Injections of the investigational product are given by an authorized healthcare professional directly at the study site, except for Week 54 when the patient self-injects the investigational product under the supervision of an authorized healthcare professional.

 The investigational product is administered only to patients from Arm 3.

 Only for patients participating in the extension study period.

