Appendix 1.

Translated from Russian to English, dated 26-Nov-2019

**Table 26.** Schedule of study visits and procedures for Arms 1 and 2 (extension treatment and follow-up periods, Weeks 54 through Week 170, starting from Week 62).

Visit	-	23	-	-	24	-	-	25	-	-	26	-	-
Week	58	62	66	70	74	78	82	86	90	94	98	102	106
Day	1±3	1±3	1±3	1±3	1±3	1±3	1±3	1±3	1±3	1±3	1±3	1±3	1±3
Information about concomitant therapy		+			+			+			+		
Blood pressure, wrist pulse, and body temperature		+			+			+			+		
Physical examination		+			+			+			+		
Body weight								+					
Complete blood count		+			+			+			+		
Blood chemistry		+			+			+			+		
hs-CRP		+						+					
Atherogenicity index (TC/HDL-C)								+					
apoB1 / apoA1								+					
Tuberculosis diagnostics								+					
Urinalysis		+			+			+			+		
ECG													
Pregnancy test		+			+			+			+		
Administration of BCD-085 at the study site		+			+			+			+		
Self-administration of BCD-085 by the patient at home	+		+	+		+	+		+	+		+	+
Dispensing the investigational product 		+			+			+			+		
Accounting of the investigational product		+			+			+			+		

 A container for used syringes is also dispensed.

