### **Procedures of Visit 8 (Day 1 of Week 12)**

- Information about concomitant therapy.
- Physical examination.
- Psoriasis Area and Severity Index (PASI), including Body Surface Area affected by psoriasis (BSA).
- Static Physician's Global Assessment (sPGA).
- [REDACTED]
- The patient fills out the VAS for itch.
- DLQI questionnaire.
- Nail Psoriasis Severity Index (NAPSI).
- Assessment of psoriatic arthritis: swollen/tender joint count(66/68), VAS by the patient (pain, disease activity) and by the physician (disease activity), functional activity with HAQ-DI.
- Unblinding.
- Taking a blood sample for immunogenicity assay [REDACTED]
- Complete blood count [REDACTED]
- Blood chemistry [REDACTED]
- hs-CRP, atherogenicity index, apoB1/apoA1 [REDACTED]
- Urinalysis.

Translated from Russian to English, dated 26-Nov-2019

- Administration of BCD-085 (only to patients from Arm 3: first administration of BCD-085).
- Blood pressure, heart rate and body temperature (immediately after dosing).
- ECG.
- Assessing injection site reactions.
- Recording AEs/SAEs.

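### Week 12 unblinding tells sites and patients who had Q2W and who had Q4W although both arms are then treated identically, so the later secondary Arm 1 versus Arm 2 comparisons lose their blind for no stated reason

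*Protocol*

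**What the plan says.** Protocol 4.3.5 blinds investigators and patients until Week 12 and then lifts the blind for every arm: "Starting from Week 12 treatment arms will be unblinded. The investigators and patients will be made aware of the drug and the dose used". Section 4.2 gives the mechanism: "Unblinding will be performed at Visit 8 (Week 12) by opening the randomization envelopes provided by the Sponsor with the investigational products". Section 4.10 says that the site-held envelopes carry the therapy-arm codes.

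The two active arms then follow one plan: "Patients from Arms 1 and 2 will be given BCD-085 once every 4 weeks". Section 4.4.1 lists the same injection weeks for both. The extension schedule in Table 26 is a single one, headed "Schedule of study visits and procedures for Arms 1 and 2". Arm 3 is the exception. A footnote to the Visit 8 dosing entry in Table 25 reads "The investigational product is administered only to patients from Arm 3", and Visit 8-1 at Week 13 exists for Arm 3 alone.

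The regimen comparison continues after Week 12. Objective 2 in Protocol 2.2 compares the two regimens and placebo after 52 weeks, and objective 3 adds "To compare the safety profiles of BCD-085 Q4W and BCD-085 Q2W". Section 4.1.2 includes "Proportion of patients who achieved PASI 75/90/100 at Weeks 8, 16, 24, 42 and 52, by study arms". Under SAP section 5, Supplementary Report 1 gives efficacy and safety by arm after 54 weeks. Protocol 1.2.3 calls the time from Week 12 open-label and concludes that blinding is not needed. It gives no reason for revealing Q2W versus Q4W.

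**The concern.** Protocol 1.5.1 justifies the double blind as protection against bias in the physician's and the patient's assessments. From Week 12 that protection is given up for the two active arms as well as for the placebo switch, although only the switch calls for it.

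An Arm 1 patient then knows that dosing has become less frequent, and an Arm 2 patient knows that it was on the sparser regimen throughout. The investigator who scores PASI, sPGA and NAPSI and judges adverse events knows it too, and the patient rates itch and DLQI. Expectations could push these scores either way. The stake is the credibility of the Week 52 regimen comparison, which is a stated objective. Investigator-scored PASI 75 at Week 52 also decides who enters the extension.

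**Working it through.** No figure in the plan bears directly on this point, so the check compares schedules and counts what is exposed.

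**1. Patients affected.** Planned arm sizes (Protocol 4.2): 85 + 85 + 43 = 213. Arms 1 and 2: 170 / 213 = 79.8%.

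**2. Dosing weeks (Protocol 4.4.1).**

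| Period | Arm 1 | Arm 2 |
|---|---|---|
| Weeks 0–10, active doses | 0, 1, 2, 4, 6, 8, 10 (7 doses) | 0, 1, 2, 6, 10 (5 doses; placebo at 4 and 8) |
| Weeks 14–50, every 4 weeks | (50 − 14)/4 + 1 = 10 | 10, same weeks |
| Weeks 54–154, every 4 weeks | (154 − 54)/4 + 1 = 26 | 26, same weeks |

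From Week 12 on, the arms share all 10 + 26 = 36 injections and differ in none. Their only difference is two active doses, at Weeks 4 and 8, both inside the blinded period. Up to Week 154, Arm 3's dosing weeks differ from theirs only at Weeks 12 and 13. The switch therefore needs one fact per patient: placebo or BCD-085. Concealing Q2W versus Q4W needs no dummy injection, extra lot or extra visit.

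**3. Comparisons exposed (Protocol 4.1.2, assessments after Week 12 in the main period).**

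- PASI 75/90/100 at Weeks 16, 24, 42, 52: 3 × 4 = 12
- sPGA 0 or 1, same weeks: 4
- sPGA 0, same weeks: 4
- Relative PASI change, same weeks: 4
- Itch at Weeks 24, 52: 2
- NAPSI at Weeks 24, 52: 2
- DLQI change at Weeks 24, 42, 52: 3
- DLQI 0 or 1 at Weeks 24, 42, 52: 3
- ACR20/50/70 at Weeks 24, 52: 3 × 2 = 6

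Total: 12 + 4 + 4 + 4 + 2 + 2 + 3 + 3 + 6 = 40, plus adverse events from Week 12 to Week 54. Only the PASI response line names the arms. The others come in through objective 2 and the by-arm report in SAP section 5.

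**4. Who does the scoring.** One investigator is to score a patient's PASI at all visits, with one replacement allowed (Protocol 4.7.8). DLQI and itch are the patient's own ratings (4.7.10, 4.7.12). No separate blinded assessor is described.

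**5. Week 12 itself.** Protocol 7.2.1 analyses the primary endpoint after 12 weeks of blinded therapy. The Visit 8 list in 4.6.2 puts PASI, sPGA, itch, DLQI, NAPSI and the arthritis assessment before unblinding, but does not make that order a rule.

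**6. Illustration only, on assumptions not in the documents.** Take equal true PASI 75 rates p of 80% to 90%, 85 patients per arm, a two-sided 0.05 test, and a scoring shift b against one arm. With s = √[p(1−p)/85 + (p−b)(1−p+b)/85], the false-positive rate is Φ(b/s − 1.96) + Φ(−b/s − 1.96). For p = 0.85 and b = 0.05, s = 0.058 and the rate is 13.8%. Over the range of p:

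- b = 2 points: 6.2% to 7.0%
- b = 5 points: 12.2% to 16.7%
- b = 10 points: 32.9% to 45.4%

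This shows sensitivity to a shift. It does not estimate one.

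**The case against.** The strongest reply is that this is an openly declared design choice with limited consequences. Nobody receives Q2W after Week 10, so the later contrasts measure what is left of two extra early doses, and they are secondary. The safety objective names no time point, and the regimens differ only in the blinded period. All of this stands and limits the weight of the point. It does not remove it: the plan still reports the arms side by side at 54 weeks, and a small carry-over difference is easily swamped by assessment bias.

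It can also be said that the wording of 4.3.5 reveals only drug and dose, which are the same in both active arms. But that section says the arms themselves are unblinded, and 4.10 speaks of arm codes. If the regimen was meant to stay hidden, a sentence should say so.

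Three practical objections stand and shape the remedy:

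- Section 4.10 describes one site-held kit and names no other. Rewording those envelopes could change what an emergency code break reveals.
- Sponsor staff allocate the arms and keep the lists (4.3.4), and the Final Report needs Week 12 results by arm (SAP section 5). Masking them until Week 52 is not realistic.
- Version 1.0 dates from October 2017 and Version 2.0 from November 2018, and 4.6.1 provides for patients who have already finished the main period. They cannot be re-masked.

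A reader might also infer that queries and outlier decisions on the primary contrast lose their blind. The documents do not support this in general. Queries come from the sponsor's data manager and medical expert, and suspected outliers go to the statistician with the medical expert and, only if needed, the principal investigator (9.6). Section 4.3.5 never promised that sponsor staff were masked. What the code opening adds is mainly the knowledge of site staff who answer queries.

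**Conclusion.** The point holds as a cheap improvement to the secondary comparisons. Sites and patients are told the regimen of 170 of 213 patients when the switch requires only placebo status. As a result, 40 Arm 1 versus Arm 2 endpoint-visits at Weeks 16 to 52, and the adverse-event comparison to Week 54, are made with the earlier regimen known. The count shows breadth, not harm: neither the size nor the direction of any bias can be derived from the documents.

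Two stronger conclusions are tempting and not supported. One is that the primary result is compromised: the Week 12 scores are listed before unblinding, and nothing shows that they are affected. The other is that no operational reason for the disclosure exists: the documents, which are partly redacted, show only that none is stated.

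The conclusion assumes that the Week 12 envelopes reveal the arm, as 4.2, 4.3.5 and 4.10 read together indicate, and that no blinded assessor is used.

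**What to change.** In Protocol 4.2, 4.3.5 and 4.10 and SAP 3.1, replace full unblinding at Week 12 with a separate card or envelope that states only BCD-085 or placebo. Keep site staff and patients masked to Q2W versus Q4W until the Week 52/54 data are locked. Sponsor staff who produce the Week 12 Final Report may be unblinded. The emergency code envelopes and the emergency procedure stay as they are.

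In the Visit 8 procedures, state that all efficacy assessments are completed before unblinding. For patients already unblinded, label the later Arm 1 versus Arm 2 comparisons as open-label.

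Cost: a second set of envelopes or cards and the amended text. No change to drug supply, visits, sample size or alpha is needed. The downsides are that sites and patients learn the past regimen later, and that patients already past Week 12 stay unmasked, so an arm may hold both masked and unmasked patients.

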### **4.4. Description of the study treatment, doses, and dosing regimen of the investigational products. Description of the dosage form, packaging, and labeling of the investigational products**

#### **4.4.1. Description of the study treatment, doses, and dosing regimen of the investigational products**

Patients in Arm 1 will receive BCD-085 120 mg given as two SC injections on Day 1 of Week 0, Week 1, Week 2, Week 4, Week 6, Week 8, Week 10 (blinded treatment period), then on Day 1 of Weeks 14, 18, 22, 26, 30, 34, 38, 42, 46, 50. If achieving  $\geq$ PASI 75 response at Week 52, patients will continue to receive BCD-085 120 mg once every 4 weeks starting from Week 54

Translated from Russian to English, dated 26-Nov-2019  
(with injections given at Weeks 54, 58, 62, 66, 70, 74, 78, 82, 86, 90, 94, 98, 102, 106, 110, 114, 118, 122, 126, 130, 134, 138, 142, 146, 150, 154).

In Arm 2, patients will receive BCD-085 120 mg as two SC injections on Day 1 of Weeks 0, 1, 2, 6, 10 (blinded treatment period). To maintain the study blind, patients of this arm will receive placebo (2 injections) on Day 1 of Week 4 and Week 8. At Week 12, treatment will be unblinded, and since then patients will continue to receive BCD-085 120 mg once every 4 weeks starting from Week 14. Thus, injections will be given at Weeks 14, 18, 22, 26, 30, 34, 38, 42, 46, and 50. If achieving  $\geq$ PASI 75 response at Week 52, patients will continue to receive BCD-085 120 mg once every 4 weeks starting from Week 54 with injections given at Weeks 54, 58, 62, 66, 70, 74, 78, 82, 86, 90, 94, 98, 102, 106, 110, 114, 118, 122, 126, 130, 134, 138, 142, 146, 150, 154.

Patients in Arm 3 will receive placebo as two 1.0 mL SC injections on Day 1 of Week 0, Week 1, Week 2, Week 4, then on Day 1 of Week 6, Week 8, Week 10 inclusive (blinded treatment period). After that, they will be switched to BCD-085 120 mg SC with injections given on Day 1 of Weeks 12, 13, 14, 18, 22, 26, 30, 34, 38, 42, 46, and 50. If achieving  $\geq$ PASI 75 response at Week 52, patients will continue to receive BCD-085 120 mg once every 4 weeks starting from Week 54 with injections given at Weeks 54, 58, 62, 66, 70, 74, 78, 82, 86, 90, 94, 98, 102, 106, 110, 114, 118, 122, 126, 130, 134, 138, 142, 146, 150, 154, 158, 162, 166.

The patients will be followed up until Week 158 (in Arms 1 and 2) or Week 170 (in Arm 3).

Regardless of the arm where the patient is assigned to, during the main study period (Week 0 through Week 54) SC injections will be performed by an authorized member of the study team at the study site (except for the injection on Week 54).

At Week 54 patients will be trained on how to self-inject the investigational product. If necessary, the training can be repeated at any of the subsequent visits.

During the extension study period (Week 54 to Week 154 for patients from Arms 1 and 2, Week 54 to Week 166 for patients from Arm 3), patients will self-inject the investigational product at home (on Day 1 of Weeks 58, 66, 70, 78, 82, 90, 94, 102, 106, 114, 118, 126, 130, 138, 142, 150 in Arms 1 and 2; on Day 1 of Weeks 58, 66, 70, 78, 82, 90, 94, 102, 106, 114, 118, 126, 130, 138, 142, 150, 158, 162 in Arm 3) after relevant training at the study site at Week 54. Injections of the investigational product on visit dates will be performed by an authorized member of the study team at Weeks 62, 74, 86, 98, 110, 122, 134, 146, 154 (in Arms 1 and 2) or at Weeks 62, 74, 86, 98, 110, 122, 134, 146, 154, 166 (in Arm 3). The first self-injection of the investigational

Injections can be given to the abdomen, hips, or upper arms. Injections should be given at least 5 cm apart. The overall duration of all three injections should not exceed 15 min from the beginning of the first injection.

#### **4.4.2. Description of the dosage form, packaging, and labeling of the investigational products**

See section 1.2. Name and description of investigational products.

##### **4.4.2.1. Test drug**

See Section 1.2.1. **Test drug**

See Section 1.2.2. **Placebo**

##### **4.4.2.3. Labeling of investigational products**

See Section 1.2.3.

#### **4.5. Expected duration of the study and subjects' participation in the study**

The expected duration of the study is 65 months, which includes patients' recruitment (up to 12 months), treatment period, follow-up period, and data collection and statistical processing. The expected duration of each subject's participation in the study, including the screening period, active study phase and follow-up period, is about 162 weeks (for patients from Arms 1 and 2) or 174 weeks (for patients from Arm 3).

#### **4.6. Description of the sequence and duration of all study periods**

##### **4.6.1 Study visits and procedures**

The study includes the following periods:

1. Screening (up to 28 days from signing the Patient Information Sheet with the Informed Consent Form, inclusive);
2. Main treatment period (from Week 0 through Week 54);
3. Extension treatment period (from Week 54 through Week 154 in Arms 1 and 2, from Week 54 through Week 166 in Arm 3);

4. Follow-up period (from Week 154 through Week 158 in Arms 1 and 2, from Week 166 through Week 170 in Arm 3).

The Investigator will decide whether it is feasible and possible to include the patient in the extension study period based on efficacy data (PASI 75), tolerability and safety of BCD-085 in each particular patient during the main study period if the patient gives his/her consent to participate in the extension study period. If by the date of approval of Protocol BCD-085-7 version 2.0 of 02-Nov-2018 the patient has completed all visits of the main treatment period, and the last injection of the investigational product at Week 50 was not more than 6 weeks ago, the Investigator should inform the patient about this Amendment and about an opportunity to continue the therapy in the extension study period, and invite the patient to come to the study site for reading and signing the new version of the Informed Consent Form (v. 2.0 as of 02-Nov-2018). If the patient agrees/refuses to visit the study site and/or is lost to follow-up, the investigator should record this in source documentation. If by the date when Protocol BCD-085-7 v. 2.0 of 02-Nov-2018 is approved the patient has not completed the main study period, the Investigator should inform the patient about this Protocol Amendment and an opportunity to participate in the extension study period, and the patient will sign the informed consent form during the planned visit. This should be recorded in the source documentation.

Table 25 lists all the procedures to be performed in the study. All data obtained during these assessments must be confirmed by the source documents.

The screening/baseline assessment should be performed within 28 days before the estimated date of the first infusion of the investigational product. Visit 1 should be within 4 days after the randomization date. Prior results may be used for certain screening tests and exams (see section 4.7 for details). CBC, blood chemistry, urinalysis, QuantiFERON (or T-Spot) can be repeated once at screening. Repeated collection of biospecimens is also allowed if the sample is lost, if any technical problems occur at the pre-analytical phase (defective sampling/storage/transportation of the material), or is the biospecimen is not suitable for analysis (e.g. due to hemolysis or milky serum). At the end of the screening period, the patient should be assessed for the inclusion/exclusion criteria and undergo randomization. The schedule of visits during the extension period is presented in Table 24.

Translated from Russian to English, dated 26-Nov-2019

**Table 24.** Schedule of visits during the extension period.

Arms 1 and 2: patients initially randomized to BCD-085 arms, Arm 3: patients initially randomized to the placebo arm			
Visit	Group 1	Group 2	Arm 3
Visit 23 (Day 1 of Week 62)	+	+	+
Visit 23-1 (Day 1 of Week 64)	Not performed	Not performed	+
Visit 24 (Day 1 of Week 74)	+	+	+
Visit 25 (Day 1 of Week 86)	+	+	+
Visit 26 (Day 1 of Week 98)	+	+	+
Visit 27 (Day 1 of Week 110)	+	+	+
Visit 28 (Day 1 of Week 122)	+	+	+
Visit 29 (Day 1 of Week 134)	+	+	+
Visit 30 (Day 1 of Week 146)	+	+	+
Visit 31 (Day 1 of Week 154)	+	+	+
Visit 32 (Day 1 of Week 158)	+	+	N/A
Visit 32-1 (Day 1 of Week 166)	Not performed	Not performed	+
Visit 32-2 (Day 1 of Week 170)	Not performed	Not performed	+

